7.0 DATA ANALYSIS AND STATISTICAL METHODS

7.1 Sample size

As this is a pilot study, no formal sample size calculation was performed. For feasibility reasons, a total of 30 participants will be enrolled with 10 in the placebo group and 20 in the active treatment group.

7.2 Randomization

The randomization scheme will be prepared by the study statistician per standard statistical procedures. Randomization will be a 2:1 ratio between mirabegron and placebo, and aim at equivalent sex distribution in the active treatment and placebo groups.

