3.2 Subject Selection

3.2.1 Number of subjects and assignment to treatment groups

A sufficient number of subjects will be screened and randomized until 30 subjects have received at least 1 dose of double-blind study medications (i.e. complete visit 3 and receive at least one dose of study drug after randomization). An effort will be made to assign equal proportions of men and women into the two treatment assignments. Randomization will be a 2:1 ratio between mirabegron and placebo.

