7.4.2 Summary of efficacy data

The first secondary objective of this project is to assess the efficacy of mirabegron for treating OAB symptoms in PD with CI. The hypothesis is that participants in the

treatment group will experience improved OAB symptoms compared to placebo group. As this is a superiority objective, a 2-sample t-test or the Mann-Whitney-Wilcoxon test will be used as appropriate to determine significant differences between treatment groups on change in OABQ subscale scores from visit 3 to visit 7. Other measures of OAB symptoms (including PPBC and the average daily values from the diary) will follow similar analyses.

The rest of the secondary objectives are to assess efficacy of mirabegron in PD and the impact of mirabegron on other non-motor symptoms in PD including health related quality of life and excessive daytime sleepiness in PD patients with OAB symptoms and CI. The related hypotheses are that mirabegron will not impact these non-motor symptoms. The goal is to demonstrate equivalent non-motor symptoms prior to and following treatment with mirabegron as well as change compared to the placebo group. Tests of equivalence will be performed using the two one-sided tests approach on change from visit 3 to visit 7 in related variables within groups as well as between the two groups. Equivalence ranges will be determined for each measure based on available literature prior to data analysis.

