Mirabegron is metabolized via multiple pathways involving dealkylation, oxidation, (direct) glucuronidation, and amide hydrolysis. Mirabegron is the major circulating component following a single dose of 14C-mirabegron. Two major metabolites were observed in human plasma and are phase 2 glucuronides representing 16% and 11% of total exposure, respectively. These metabolites are not pharmacologically active toward beta-3 adrenergic receptor. Although *in vitro* studies suggest a role for CYP2D6 and CYP3A4 in the oxidative metabolism of mirabegron, *in vivo* results indicate that these isozymes play a limited role in the overall elimination. In healthy subjects who are genotypically poor metabolizers of CYP2D6, mean C_{max} and AUC_{tau} were approximately 16% and 17% higher than in extensive metabolizers of CYP2D6, respectively. *In vitro* and *ex vivo* studies have shown the involvement of butylcholinesterase, uridine diphospho-glucuronosyltransferases (UGT) and possibly alcohol dehydrogenase in the metabolism of mirabegron, in addition to CYP3A4 and CYP2D6.

Excretion

Total body clearance (CL_{tot}) from plasma is approximately 57 L/h following intravenous administration. The terminal elimination half-life ($t_{1/2}$) is approximately 50 hours. Renal clearance (CL_R) is approximately 13 L/h, which corresponds to nearly 25% of CL_{tot} . Renal elimination of mirabegron is primarily through active tubular secretion along with glomerular filtration. The urinary elimination of unchanged mirabegron is dose-dependent and ranges from approximately 6.0% after a daily dose of 25 mg to 12.2% after a daily dose of 100 mg. Following the administration of 160 mg ^{14}C -mirabegron solution to healthy volunteers, approximately 55% of the radioactivity dose was recovered in the urine and 34% in the feces. Approximately 25% of unchanged mirabegron was recovered in urine and 0% in feces.

Specific Populations

Geriatric Patients

The C_{max} and AUC of mirabegron following multiple oral doses in elderly volunteers (\geq 65 years) were similar to those in younger volunteers (18 to 45 years).

Pediatric Patients

The pharmacokinetics of mirabegron in pediatric patients have not been evaluated [see Use in Specific Populations (8.4)].

Gender

The C_{max} and AUC of mirabegron were approximately 40% to 50% higher in females than in males. When corrected for differences in body weight, the mirabegron systemic exposure is 20% - 30% higher in females compared to males.

Race

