Interval								
p-value		0.003#		0.026#		0.005#	0.001#	
Number of Mic								
n	480	473	433	425	415	410	426	
Baseline	11.71	11.65	11.51	11.80	11.48	11.68	11.66	
(mean)	-							
Change from baseline	l				1			
(adjusted	-1.34	-1.93	-1.05	-1.66	-1.18	-1.65	-1.60	
mean [†])	l							
Difference								
from	l				1			
placebo		-0.60		-0.61		-0.47	-0.42	
(adjusted	l				1			
mean [†])					 			
95%	l				1	(000 013)	(0.76 0.00)	
Confidence Interval	-	(-0.90, -0.29)	-	(-0.98, -0.24)		(-0.82, -0.13)	(-0.76, -0.08)	
p-value	 	<0.001#		0.001#	+	0.007#	0.015#	
Volume Voide	d (mI) ner			0.001#		0.007#	0.015#	
n	480	472	433	424	415	410	426	
Baseline								
(mean)	156.7	161.1	157.5	156.3	164.0	165.2	159.3	
Change from								
baseline	12.3	24.2	7.0	18.2	8.3	12.8	20.7	
(adjusted	12.5	24.2	7.0	10.2	8.3	12.0	20.7	
mean [†])								
Difference	l							
from	l	11.0		11.1		4.6	12.4	
placebo (adjusted	-	11.9		11.1	-	4.0	12.4	
(adjusted mean [†])	l							
95%					+			
Confidence		(6.3, 17.4)		(4.4, 17.9)		(-1.6, 10.8)	(6.3, 18.6)	
Interval		,,		,,		,,,	, , , , , ,	
p-value		< 0.001#		0.001#		0.15	<0.001#	

Week 12 is last observation on treatment

Myrbetriq 25 mg was effective in treating the symptoms of OAB within 8 weeks, and Myrbetriq 50 mg was effective in treating the symptoms of OAB within 4 weeks. Efficacy of both 25 mg and 50 mg doses of Myrbetriq was maintained through the 12-week treatment period.

 $[\]dot{\uparrow}$ Least squares mean adjusted for baseline, gender, and geographical region

^{*}For incontinence episodes per 24 hours, the analysis population is restricted to patients with at least 1 episode of incontinence at baseline.
#Statistically significantly superior compared to placebo at the 0.05 level with multiplicity adjustment

Figures 3 through 8 show the co-primary endpoints, mean change from baseline (BL) over time in number of incontinence episodes per 24 hours and mean change from baseline over time in number of micturitions per 24 hours, in Studies 1, 2 and 3.

Figure 3. Mean (SE) Change from Baseline in Mean Number of Incontinence Episodes per 24 Hours –Study 1

[figure not shown]

Figure 4. Mean (SE) Change from Baseline in Mean Number of Micturitions per 24 Hours - Study 1

[figure not shown]

Figure 5. Mean (SE) Change from Baseline in Mean Number of Incontinence Episodes per 24 Hours - Study 2

[figure not shown]

Figure 6. Mean (SE) Change from Baseline in Mean Number of Micturitions per 24 Hours - Study 2

[figure not shown]

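### The allocation aims to balance sex, but no between-arm test includes it; if balance is enforced and sex predicts change, the tests are conservative

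*Combined protocol and SAP*

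**What the plan says.** Section 3.2.1: "An effort will be made to assign equal proportions of men and women into the two treatment assignments". Section 7.2: the scheme will "aim at equivalent sex distribution in the active treatment and placebo groups". Sex is the only factor named for balancing. On method, 7.2 says only: "The randomization scheme will be prepared by the study statistician per standard statistical procedures". It names no strata, blocks or minimisation.

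Sections 7.4.1 and 7.4.3 compare arms on change from visit 3 to visit 7 by two one-sided tests. For the primary MoCA outcome, 7.4.1 specifies a t-test or a non-parametric alternative and a range of (-2, 2). For bladder symptoms, 7.4.2 says "a 2-sample t-test or the Mann-Whitney-Wilcoxon test will be used as appropriate"; for its other outcomes it uses two one-sided tests. None of these includes sex. Section 7.4 mentions sex only as a possible subgroup.

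Section 7.1 plans 20 active and 10 placebo participants with no formal sample size calculation. Section 7.3 excludes withdrawn participants from the analyses.

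**The concern.** A factor used to constrain allocation normally belongs in the analysis. Once the arms are forced to have the same sex mix, sex differences in outcome cancel from the arm contrast. A two-group test still leaves them in the residual variance, so its standard error can exceed the true one. Equivalence and superiority would then both be declared less often than the design allows.

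There is also a gap on the design side. An aim or an effort is not an allocation procedure. As written, the plan does not show how balance is obtained, or how assignment stays free of discretion while it is pursued.

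**Working it through.** The plan has no power or precision figure to reproduce. The one check available is the split: 30 at 2:1 gives 20 + 10, as section 7.1 states.

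**Inputs from the documents:** 20 vs 10; significance level 0.05 (7.4); margin ±2 MoCA points (7.4.1).

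**Assumptions, not in the documents:** 18 men and 12 women; R², the share of outcome variance explained by sex, from 0 to 0.20; SD of MoCA change σ = 2, 2.5 or 3.

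**Case A: balance enforced (12/6 men, 8/4 women).** Sex cancels from the contrast, so

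- true variance = σ²(1 − R²)(1/20 + 1/10).

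The pooled residual variance keeps the sex sum of squares on 28 degrees of freedom, so

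- E(s²) = σ²[(1 − R²) + (30/28)R²] = σ²(1 + R²/14).

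The ratio of reported to true SE is therefore about √[(1 + R²/14)/(1 − R²)]. The size of a nominal two-sided 5% test is about P(|t₂₈| > 2.048 × ratio).

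| R² | SE ratio | Size, formula | Size, simulated | Equivalence power, unadjusted vs with sex (σ = 2.5, true difference 0) |
|---|---|---|---|---|
| 0 | 1.000 | 5.0% | 5.0% | 29.6% vs 29.4% |
| 0.05 | 1.028 | 4.4% | 4.4–4.5% | 30.0% vs 33.2% |
| 0.10 | 1.058 | 3.9% | 3.9% | 30.1% vs 36.7% |
| 0.15 | 1.090 | 3.4% | 3.3% | about 31% vs 41% |
| 0.20 | 1.126 | 2.9% | 2.8% | 31.9% vs 46.0% |

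Simulations used 40,000 trials per cell. With sex in the model, size returns to about 5%. Dropping the small 30/28 factor gives 1/√(1 − R²) = 1.026 and 1.054 at R² = 0.05 and 0.10, so the excess at 0.10 is 5% to 6% depending on the convention.

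At R² = 0.10, power is 63.5% vs 68.5% for σ = 2 and 8.9% vs 13.2% for σ = 3.

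**Case B: balance not enforced.** At σ = 2.5, the reported and true unadjusted SEs agree: 0.968 and 0.968 at R² = 0; 0.969 and 0.969 at 0.10; 0.972 and 0.972 at 0.20. Size is 5.1%, 4.9% and 5.1%. Equivalence power, unadjusted vs with sex, is 29.7% vs 27.1% at R² = 0, 29.3% vs 30.2% at 0.05, 29.1% vs 34.3% at 0.10 and 28.7% vs 42.9% at 0.20. Here adjustment helps when sex predicts change and costs a little when it does not, because chance imbalance makes arm and sex partly collinear.

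**Chance imbalance in Case B.** Let X be the number of men among the 10 placebo participants. The gap in male share is |X/10 − (18 − X)/20| = 0.15|X − 6|. A gap of 30 points or more needs X ≤ 4 or X ≥ 8. The hypergeometric probability is 0.118 + 0.117 = 0.235. A gap above 30 points (X ≤ 3 or X ≥ 9) has probability 0.045.

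**The case against.** A reader might infer that the planned standard errors simply are too wide. The documents do not support that. The text speaks only of an aim and an effort, and without an enforced scheme the unadjusted test holds its level (Case B). Section 7.3 also removes withdrawn participants, so even enforced balance need not survive into the analysed set. This objection stands, and the conclusion is conditional because of it.

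Nor do the documents show that sex predicts change, least of all on the MoCA. Two parts of the appended label (Appendix I) are tempting evidence. Its section 14 footnote reads "Least squares mean adjusted for baseline, gender, and geographical region", but it gives no size for any sex effect and concerns bladder outcomes. Its section 12.3 reports Cmax and AUC "approximately 40% to 50% higher in females than in males" (20% to 30% after weight correction). That applies only to people taking the drug, so it bears on a treatment-by-sex interaction rather than on a sex effect common to both arms. Neither supplies an R², and zero belongs in the range.

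It is also fair to say that the error is on the safe side, that this is a pilot with no powered claim, and that the 23% figure is mostly gaps of exactly 30 points, which means two placebo men away from the expected six. All of that limits the size of the point. It does not remove the need to state the allocation method or to match the analysis to it.

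**Conclusion.** The point holds conditionally. The plan names sex as its one balancing factor, does not say how balance will be achieved, and ignores sex in every between-arm test.

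- **If balance is enforced and sex predicts change**, the tests are conservative by the amounts in Case A, and adjustment recovers power. At R² = 0 adjustment costs essentially nothing.
- **If balance is not enforced**, the standard errors are right on average. The stated aim then often fails by chance, and adjustment is a precision gain or a small loss depending on whether sex matters.

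Neither case inflates false positives. Where the rank alternative is used, the loss is of efficiency rather than an overstated standard error. The figures rest on the assumed 18/12 split, R² and SD. Adjustment for sex does not make a 20 vs 10 equivalence comparison well powered: at σ = 2.5 and R² = 0.05 it moves power only from about 30% to 33%.

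**What to change.** **Sections 3.2.1 and 7.2.** Replace the aim and the effort with a stated procedure: a randomization list stratified by sex, with concealed 2:1 permuted blocks of varied size (for example 3 and 6). Fixed blocks of three at a single site would be too predictable.

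**Sections 7.4.1 to 7.4.3.** Include sex in each between-arm comparison:

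- a linear model with arm and sex for the t-test and two one-sided test analyses;
- a sex-stratified rank test where the non-parametric alternative applies, run at each margin for equivalence.

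**Cost.** One degree of freedom (28 to 27) and slight extra work on the list. No new data are needed, because sex is already recorded.

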7.3 Analysis population

The analysis population is based on intent-to-treat and will consist of all participants who received at least one dose during the double-blind placebo-controlled phase. Participants who withdraw from the study or are withdrawn by the study PI will be described by screening/baseline characteristics, but excluded from analyses.

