Descriptive statistics will be performed. The primary group for analysis will consist of all subjects who received at least one dose during the double-blind placebo-controlled phase. Analyses will compare change from randomization (visit 3) to end of treatment (visit 7). Tests of equivalence will be performed on primary, secondary and exploratory outcomes, with significance level of p<.05.

Study Procedures:

Refer to the Study Schedule/Flowchart, below.

Number of Subjects: 30 (20 active treatment, 10 placebo group).

Eligibility criteria:

INCLUSION CRITERIA:

- 1. Aged 25-80 at screening. Subjects older than 80 will be allowed at the discretion of the PI.
- 2. Ambulatory (defined as able to ambulate at least 10 meters, with or without assistance).
- 3. Clinical Diagnosis of PD based on the United Kingdom Brain Bank diagnostic criteria for PD.
- 4. At baseline visit (Visit 2) patients must have:
 - a. At least 8 micturitions per 24 hours and

- b. At least 3 urgency episodes per 3-day diary.
- 5. A MoCA score between 19 and 28 (inclusive) at screening. For those on cognitive enhancers (donepezil, rivastigmine, memantine, galantamine) a MoCA score between 19 and 29 (inclusive) at screening.
- 6. Provide informed consent to participate in the study and understand that they may withdraw their consent at any time without prejudice to their future medical care.
- 7. Be cognitively capable, in the opinion of investigator, to understand and provide such informed consent.
- 8. Be cognitively capable to complete the required questionnaires and assessments, OR have a care partner who is willing and capable to assist them in the completion of these tasks.
- 9. Be on a stable regimen of antiparkinson's medications at least 30 days prior to screening, and be expected to remain on a stable dose for the duration of the study.
- 10. If taking cognitive enhancers (donepezil, rivastigmine, memantine, galantamine), must be on stable dose at least 30 days prior to screening, and be expected to remain on a stable dose for the duration of the study.

EXCLUSION CRITERIA:

- 1. Known or suspected alcohol or substance abuse in the preceding 12 months.
- 2. Women who are pregnant or breastfeeding.
- 3. Women of childbearing potential (WOCP) who are not using at least one method of contraception.
- 4. Patients with severe renal impairment ($CL_{cr} \le 29 \text{ mL/min}$, or eGFR ≤ 29 mL/min/1.73 m²), or moderate or severe hepatic impairment (Child-Pugh classes B or C).

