3.5 Criteria for study discontinuation or early treatment termination

Study discontinuation may occur as a result of a decision from regulatory authorities, change of the opinion of the Park Nicollet Institutional Review Board (IRB), safety concerns raised by the Data and Safety Monitoring Committee (DSMC), or unavailability of the study drug.

The investigator retains the right to terminate the study at any time and for any reasons. Such study termination, however, will be subject to adequate consideration of the subjects' interests.

Individual subjects will be terminated from the study if they withdraw consent. In that instance, every effort will be made for the subject to attend an early termination visit and safety follow up.

Subjects may be withdrawn from the study at the discretion of the Investigator, for considerations relating to subject safety, or for non-adherence or loss of ability to comply with study requirements.

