3.9.7 End of treatment / Early termination visit (Visit 7; Day 84)

During Visit 7, screening and baseline safety and tolerability as well as efficacy and outcome measures will be repeated.

- Concomitant medications
- Adverse events
- Study drug compliance
- Vital signs, weight, height, and orthostatics
- Physical Examination
- Neurological Examination
- ECG
- UPDRS
- Blood samples for chemistry and hematology (Na, K, Cl, HCO₃, blood glucose, BUN, creatinine, GFR, AST, ALT, total bilirubin, Alkaline phosphatase, GGT, CBC with differential and platelets)
- Urinalysis
- OABO
- 3-day VD assessment
- PPBC
- CQ

- UPDRS-6
- MoCA
- Map Search
- Hopkins Verbal Learning Test (HVLT)
- Trail Making Test (TMT) parts A and B
- Beck Anxiety Inventory (BAI)
- Beck Depression Inventory version II (BDI-II)
- Epworth Sleepiness Scale (ESS)
- Parkinson Fatigue Scale (PFS)
- Parkinson's Impact Scale (PIMS)

If a subject at any point during the study requests to withdraw from treatment, they should return for an early termination visit. The procedures of visit 7 and visit 8 can be combined in a single visit for early termination subjects. It would be desirable that subjects continue to receive study drug until early termination procedures can be completed.

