3.9.9 Unscheduled visit

Unscheduled visits can be conducted at the Investigator's discretion. Procedures during these visits will be focused to the problem that precipitated the visit. If a subject develops intolerable side effects during the treatment period, but wishes to continue in the study, he/she may come in for an unscheduled visit. A dose reduction is permitted only once during treatment and only after the dose escalation to mirabegron daily dose of 50 mg vs. placebo. The dose can be decreased at that time to 25 mg of mirabegron vs. placebo. Subjects that require such dose reduction will be receiving one tablet daily. Further dose reductions will not be permitted, and, if deemed necessary, subjects will be brought in for early termination.

Changes in the antiparkinsonian agents or cognitive enhancers will only be permitted to a limited degree, and only if, in the opinion of the investigator, are not likely to alter the outcome measures of the study. Naturally, if these medication changes are triggered by worsening of the PD or cognitive symptoms, such worsening will have to be logged as an adverse event or serious adverse event as appropriate.

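### Section 7.3 names an intent-to-treat set and then excludes everyone who withdraws, which contradicts the synopsis and can bias the primary MoCA test toward equivalence

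*Combined protocol and SAP*

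**What the plan says.** Section 7.3 opens with "The analysis population is based on intent-to-treat and will consist of all participants who received at least one dose" in the double-blind phase. The synopsis, under Statistical Analysis, agrees: "The primary group for analysis will consist of all subjects who received at least one dose during the double-blind placebo-controlled phase". The second sentence of 7.3 then states: "Participants who withdraw from the study or are withdrawn by the study PI will be described by screening/baseline characteristics, but excluded from analyses".

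Nothing elsewhere restores the withdrawn subjects. Section 7.4 rules out imputation and only counts and describes those who withdraw. Section 7.4.6 does not replace anyone after randomization.

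The protocol nevertheless plans to collect their outcome. Section 3.9.7 makes Visit 7 the early-termination visit as well, with the MoCA among its procedures: "If a subject at any point during the study requests to withdraw from treatment, they should return for an early termination visit". For subjects who withdraw consent, Section 3.5 adds: "In that instance, every effort will be made for the subject to attend an early termination visit and safety follow up".

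The primary test (Section 7.4.1) applies two one-sided tests to MoCA change from Visit 3 to Visit 7, within groups and between groups, with a range of (-2, 2).

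**The concern.** There are two problems.

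First, the primary analysis set depends on which sentence is followed. Two statisticians could report different primary results from the same data, and each could cite the protocol.

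Second, exclusion can depend on the outcome. Section 3.5 lets the investigator withdraw subjects "for considerations relating to subject safety, or for non-adherence or loss of ability to comply with study requirements". On a second dose reduction, Section 3.9.9 says: "Further dose reductions will not be permitted, and, if deemed necessary, subjects will be brought in for early termination". Intolerance (6.1.8), non-compliance (6.1.10) and need for a prohibited medication (6.1.12) are further routes. Cognitive decline could lead to several of these. Subjects who stay in at the lower dose level are still analysed, so those removed are the ones who could not continue. A tolerability analysis that drops subjects who did not tolerate treatment is selected on what it measures. The within-mirabegron test has no comparator to offset this.

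The terms are also unclear. Section 7.3 speaks of leaving the study and Section 3.9.7 of leaving treatment. The plan does not say whether a subject who stops drug but completes Visit 7 is analysed.

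**Working it through.** **Inputs from the documents.** 20 mirabegron and 10 placebo (7.1); margin ±2 points (7.4.1); significance level 0.05 (7.4), taken here as 0.05 for each one-sided test, so equivalence means the 90% interval lies inside (-2, 2). Section 7.1 states that no formal sample size calculation was made, so there is no power figure to reproduce.

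**Assumed.** SD of MoCA change (2.5, with 2 and 3 as alternatives), the withdrawal pattern, and normally distributed changes.

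**Worked example.** SD 2.5 in each arm; mean change -0.5 on mirabegron and 0 on placebo; two mirabegron subjects lost 5 points each.

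- All 30: SE = 2.5 × √(1/20 + 1/10) = 0.968; t(28) = 1.701; half-width 1.647. Interval -0.5 ± 1.647 = (-2.15, 1.15). Equivalence is not shown.
- Exclude one: mirabegron mean = (-10 + 5)/19 = -0.26; pooled SD 2.39; half-width 1.59. Interval (-1.85, 1.32). Equivalence is shown.
- Exclude both: mean = (-10 + 10)/18 = 0; mirabegron SD falls from 2.5 to 2.08; pooled SD 2.24; half-width 1.50. Interval (-1.50, 1.50). Equivalence is shown.

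If those two had no MoCA, the conclusion would tip at an assumed loss of about 4.2 points each.

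**Simulation.** True mean change -2 on mirabegron (on the margin) and 0 on placebo, SD 2.5, 60,000 trials per cell. Subjects whose change is -4 or worse leave with probability 25/50/100% and are excluded. With everyone kept, false equivalence is about 4% between arms and 5% within mirabegron.

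| Who leaves | Between arms | Within mirabegron |
|---|---|---|
| Observed decliners, both arms | 6/8/17% | 9/18/57% |
| Observed decliners, mirabegron only | 6/10/22% | 9/18/57% |
| True decliners, both arms, half the variance noise | 5/6/9% | 7/9/18% |

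With 70% of the variance as noise, the 100% case for true decliners is about 6% between arms and 9-10% within mirabegron. The true-change rows are closer to this trial: Table 1 has no MoCA between Visits 3 and 7, so leaving can only follow noticed symptoms and not the score itself.

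At other SDs (observed change, both arms), the between-arm rates are 7/9/17% at SD 2, against 5% with all kept, and 3/4/13% at SD 3, against 2%.

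**Other patterns of loss.** If only placebo decliners leave, the between-arm rate falls to 3.6/3.1/2.1%. Random dropout of 10/20/30% gives 3.7/2.9/2.2%. With a true effect of 0, random dropout lowers the chance of showing between-arm equivalence from 29% to 22/15/10%.

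**The case against.** The strongest reply is about size. In the more realistic scenario the between-arm rate is 5/6/9% against 4%, and even 9% needs every true decliner of 4 or more points to leave. The larger figures require leaving to follow a Visit 7 score that nobody has yet seen. This stands: the extreme rows are bounds, not forecasts.

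The trigger is also hypothetical. No section makes cognitive decline itself a withdrawal criterion. Section 1.3 reports no central nervous system adverse events in the mirabegron trials, and the discontinuation reactions listed in Section 6.1.2 include no cognitive event. Those trials enrolled general overactive-bladder patients, however, and tolerability in cognitively impaired Parkinson patients is the question here.

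The worked example partly reflects low precision. At SD 2.5 the observed difference must lie within ±0.35 (2 - 1.647) for equivalence to be shown with all 30. That is fair, but it also shows why one excluded subject can decide the result.

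A narrower reading would analyse a subject who stops drug and attends Visit 7, since 7.3 refers to leaving the study. The text permits this reading, but it does not rescue subjects whom the PI withdraws.

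Finally, cognitive worsening would still appear among adverse events by group (7.4.4). That is useful, but it does not repair the primary test.

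**Conclusion.** The concern holds. The contradiction is in the text and concerns the primary analysis set. It is a stated rule that is wrong as written, not missing detail, and pilot status does not excuse it because Section 7.4.1 specifies a formal equivalence test with a fixed margin.

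The direction of bias is conditional. It runs toward equivalence if mirabegron subjects leave because of cognitive decline, the other way if placebo decliners leave, and random loss costs power only. Its size cannot be derived from the documents. Under the assumptions above, between-arm false equivalence goes from about 4% to 5-9% in the milder case and to 17-22% at the extreme. Within mirabegron it goes from 5% to 7-18% and to 57%. The conclusion rests on the contradiction and the direction of bias, not on the extreme figures.

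**What to change.** **Section 7.3.** Delete the clause that excludes withdrawn participants. Analyse everyone with at least one double-blind dose in the randomized arm. Use the early-termination MoCA as the end-of-treatment value where it exists, and state that this covers both stopping treatment and leaving the study.

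**Section 7.4.** Amend the no-imputation rule to allow one tipping-point sensitivity analysis:

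1. Mirabegron subjects with no post-randomization MoCA: assume a change of 0, -1, down to -6.
2. Mirabegron subjects with only an early-termination MoCA: subtract 0, 1, 2 and so on from their change.
3. Placebo subjects: keep the early-termination value; if there is none, assume 0, then repeat with the placebo completers' mean.

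Report where the 90% interval leaves (-2, 2). A simpler grid would also serve. Tabulate withdrawals by arm and reason, and report completers as supportive.

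**Cost.** Text changes, IRB approval of the amendment (Section 9.3), one extra analysis and two table columns. No new visit or procedure.

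**Limit.** The bias is reduced, not necessarily removed. An early-termination MoCA after short exposure can dilute a true effect, and staying on drug until that visit is only a wish: "It would be desirable that subjects continue to receive study drug until early termination procedures can be completed". With observed decliners leaving both arms and all their values kept, between-arm false equivalence is 6/7/12% if leavers show none of the effect, 5/6/7% if half, and 4% if all. If half the leavers have no MoCA and the rest show none of the effect, the main analysis gives 6/7/14% between arms and 8/13/35% within mirabegron. The sensitivity row that sets missing mirabegron changes to -4, missing placebo changes to 0, and subtracts 2 from mirabegron early-termination changes gives 4/5/5% and 6/6/8%. The sensitivity analysis should therefore accompany the corrected set.
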